7.2.2.2 Imputation Rules for Missing or Partial Medication Start/Stop Dates

Missing or partial medication start date:

- If only Day is missing, use the first day of the month.
- If Day and Month are both missing, use the first day of the year, i.e., 01 January.
- If Day, Month and Year are all missing, use the day before the first dose date.

Missing or partial medication stop date:

- If only Day is missing, use the last day of the month.
- If Day and Month are both missing, use the last day of the year.
- If Day, Month and year are all missing, assign ‘continuing’ status to stop date

8 STATISTICAL METHODS

8.1 General Statistical Conventions

All statistical procedures will be completed using SAS version 9.4 or higher.

The statistical analysis of the IA will be performed after all subjects finalize the re-evaluation for retreatment visit at week 16 of the first treatment cycle or complete the double-blind phase (whichever occurs earlier). Unblinding will occur when the analysis populations have been determined based on a blinded data review after database closure for all data belonging to the double-blind phase up to and including the re-evaluation for retreatment visit at week 16.

The statistical analysis of the final analysis of the first treatment cycle and the open label extension phase (cycles 2 to 4) will be performed after database lock of all data up to the end of the study.

The statistical testing of the primary efficacy endpoint as well as the key secondary efficacy endpoint will be one-sided and will be performed using a significance (alpha) level of 0.025. A two-sided McNemar test (using a significance level of 0.05) will be used to compare the response proportions between week 4 re-treatment visit and at the preceding end of the cycle visit. This endpoint will be separately analyzed for each open label extension cycle. Two-sided 95% CIs will be provided when relevant.

Continuous variables will be summarized using descriptive statistics, including number of subjects (n), mean, standard deviation (SD), median, minimum and maximum. One additional decimal point for mean and median and two additional decimal points for SD will be used in addition to the number of decimal points used for the measured values.

For categorical variables, summaries will include counts of subjects and percentages in corresponding categories. Percentages will be rounded to one decimal place.

For statistical analyses “baseline” refers to the last observation before treatment, i.e., pre-treatment values measured on the treatment day (baseline visit, day 0), and if missing or not evaluated, values from screening visit will be used.

All summaries will be presented by treatment group, unless otherwise specified.

Analyses will be performed by visit, irrespective of any time window deviations.

All subject data, including those derived, will be presented in individual subject data listings. Unless otherwise stated, unscheduled visit results will be included in date/time chronological order, within subject listings only. All listings will be sorted by investigational site, subject number, date/time and visit. The treatment group will be stated on each listing. Unless

Statistical Analysis Plan (SAP)

CROMA
est. 1976

otherwise stated, data listings will be based on the SAF population. A listing with demographic data for screening failures will be presented.

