9.3.1 Unscheduled Visit

An unscheduled visit can be held at any time during the study, if deemed necessary by the investigator. In addition, an unscheduled visit must be scheduled to occur as soon as possible if an AESI is reported during any telephone contact. An unscheduled visit will not replace any of the above visits as per schedule of events. Assessments performed at an unscheduled visit

will be at the investigator's discretion, but should include AE assessment, AESI query, concomitant medication and possibly FWS.

In case of an unscheduled visit, the investigator should complete the "Unscheduled Visit Form" in the CRF.

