11.15 Clinical Laboratory Tests (Safety)

A full list of the parameters that will be analyzed can be found below.

Any safety laboratory results outside the normal range will be evaluated by the investigator or his designee as "clinically significant" or "not clinically significant". Any test assessed as being clinical significant must be documented as pre-treatment event (if obtained at Screening) or as AE. Sites will conduct re-tests for blood samples which could not be analyzed at the central lab due to e.g. haemolysis etc. Repeat of lab tests for clinically significant test results are at the discretion of the investigator.

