7 STATISTICAL CONSIDERATIONS AND ANALYSIS

7.1 Derived Variables

The below table provide the list of derived variables for various duration derivations and baseline derivations applicable for this study.

Variables	Formula
Derivation of Duration	
Study day at any visit	Date of interest – date of first dose of study drug, if date of interest is before date of first dose of study drug. Date of interest – date of first dose of study drug + 1, otherwise.
Extent of Exposure (Days)	Last exposure date – Date of first study medication administration + 1 where Last exposure date = Maximum of (last study medication administration date, last visit date, end of study date).
Extent of Exposure (Weeks)	Extent of exposure (days)/7
Baseline Derivations	
Baseline	The baseline value is defined as the last observation before treatment, i.e., pre-treatment values measured on the treatment day (baseline visit, day 0), and if missing or not evaluated, the value from screening visit.
Change from baseline	Post baseline value – Baseline value
Relative change from baseline	$[(\text{Post baseline value} - \text{Baseline value})/\text{Baseline value}] * 100$

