8.7 Safety Analyses

This section describes the safety analyses that will be conducted on the double blind and the open label treatment period, i.e., the safety analyses on all data collected during these treatment periods and all data collected in subjects who dropped-out during one of the treatment periods.

All definitions relative to safety endpoints are detailed in the following sections.

Safety analyses will be conducted on the SAF population and will be performed for all safety variables specified below.

All safety data will be summarized by treatment group.

The safety analyses of changes from baseline to a specific time point in safety variables (e.g., laboratory parameters, vital signs, and ECG) will only include subjects from the SAF population who have data available for both the baseline and the time point under consideration unless otherwise specified.

No statistical testing methods will be applied to statistically evaluate the differences on safety variables between treatment groups. Safety endpoint variables will be analyzed descriptively only.

An additional safety evaluation will be performed for laboratory data, vital signs, and ECG by defining cycle 2 day 0 as baseline (or last available value before drug administration of Cycle 2) for all subjects.

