8.7.4 Laboratory Data

For the purposes of summarization in both the tables and listings, all laboratory values will be presented in SI units. If a lab value is reported using a nonnumeric qualifier e.g., less than (<) a certain value, or greater than (>) a certain value, the given numeric value will be used in the summary statistics, ignoring the nonnumeric qualifier.

Visit value and change and/or percent change from baseline (where applicable) during the treatment period will be summarized by treatment group using descriptive statistics for all laboratory parameters.

All laboratory values will be classified as normal or abnormal according to the central laboratory normal ranges and indicated as clinically significant (CS) or not clinically significant (NCS) by the investigator. Categorical variables will be summarized by counts and percentages of subjects in corresponding categories. Shift tables illustrating changes with respect to the central laboratory normal ranges and the investigator assessment between baseline and post-baseline visits will be created: number and percentage of subjects with normal, CS and NCS laboratory values.

Statistical Analysis Plan (SAP)

CROMA
est. 1976

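### Laboratory shift tables merge low with high abnormal values, and unscheduled laboratory and vital-sign results that are not judged clinically significant reach no summary table

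*SAP*

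**What the plan says.** **Shift categories.** SAP 8.7.4 classes each laboratory value as normal or abnormal against the central laboratory range. The investigator marks abnormal values as CS or NCS. The shift tables then give the "number and percentage of subjects with normal, CS and NCS laboratory values". No low or high category is named.

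**Unscheduled results.** SAP 8.1, unless otherwise stated: "unscheduled visit results will be included in date/time chronological order, within subject listings only". This is a default that other text may override. SAP 8.7.4 states no exception for laboratory data. SAP 8.7.5 ties vital-sign changes to the scheduled time points.

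**Re-tests.** Protocol 11.15: "Sites will conduct re-tests for blood samples which could not be analyzed at the central lab due to e.g. haemolysis etc". Protocol 9.3.1, on unscheduled visits in general: "An unscheduled visit will not replace any of the above visits as per schedule of events". SAP 8.1 on visit assignment: "Analyses will be performed by visit, irrespective of any time window deviations".

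**Baseline.** The footnote to the schedule in both documents makes the screening laboratory sample the baseline. SAP 7.1 opens broadly and then narrows, "The baseline value is defined as the last observation before treatment, i.e., pre-treatment values measured on the treatment day (baseline visit, day 0", with the screening visit as fallback. SAP 8.7 limits change analyses to subjects "who have data available for both the baseline and the time point under consideration", unless otherwise specified.

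**The concern.** A laboratory shift table is meant to show how many subjects moved, and in which direction, relative to the reference range. Without direction it cannot separate a treatment that pushes a parameter up from random movement both ways. Among abnormal values it also treats a complete reversal as no movement.

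The listings-only rule adds to this. Values taken outside the schedule are often taken because someone had a reason to look. If such a value is abnormal but not CS, it generates no adverse event, so the adverse event tables do not pick it up either.

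Long-term safety, and a safety database sufficient for approval, is a stated secondary objective (Protocol 5.3, SAP 2.2), so the safety tables should use what was collected. Timing also matters. The interim safety outputs in SAP 8.9 are adverse event and AESI tables, so the laboratory and vital-sign tables come at the final analysis, after the double-blind phase has been unblinded. A rule not written down before then would be settled with treatment known.

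**Working it through.** No figure in the plan needs reproducing here. The check is a count of table cells and a trace through the rules.

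**1. What the shift table can distinguish.**
- With direction kept, a value is in one of five states: low CS, low NCS, normal, high NCS, high CS. Baseline by post-baseline gives 5 × 5 = 25 possible moves.
- The planned table has three states, so 3 × 3 = 9 cells.
- Moves per planned cell: normal to normal 1; normal to NCS, normal to CS, NCS to normal and CS to normal 2 each; NCS to NCS, NCS to CS, CS to NCS and CS to CS 4 each. Total: 1 + 4 × 2 + 4 × 4 = 25.
- Only the normal-to-normal cell keeps its meaning. The NCS-to-NCS cell holds low to low, high to high, low to high and high to low, so two of its four moves are reversals that appear as no shift.
- The normal-to-NCS cell holds both normal to low and normal to high. If one arm had only the first and the other only the second, in equal proportion, the two columns would be identical.

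**2. Where an unscheduled laboratory or vital-sign value can appear.**
- By-visit values, changes and laboratory shifts: excluded by the SAP 8.1 default, since 8.7.4 and 8.7.5 state no exception.
- Adverse event tables: only if judged CS. Protocol 11.1.1 and 11.15 make such a finding an adverse event, or at screening a pre-treatment or medical history entry.
- Listings: yes.
- An abnormal, non-CS value at an unscheduled visit is therefore in the listings and in no summary table.

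**3. Where a re-test of an unusable sample can appear.** Neither document gives it a visit label. The End of Study mapping in SAP Appendix A is restricted to the efficacy dataset, so it does not help.
- *Filed under the visit it replaces.* SAP 8.1 analyses by visit whatever the timing, so the value is tabulated. A screening re-test is a screening sample and serves as baseline.
- *Filed as unscheduled.* The value goes to listings. A pre-dose re-test fits the opening of the baseline definition but neither of the two sources that the definition then names. If it is not accepted, SAP 8.7 removes the subject from change-from-baseline analyses of the affected parameters.
- For the additional Cycle 2 safety evaluation, SAP 8.7 does accept the last available value before the Cycle 2 dose. The main baseline has no equivalent wording.

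**The case against.** **Direction is not lost altogether.** SAP 8.7.4 also summarises values and changes by visit for every laboratory parameter, with mean, SD, median, minimum and maximum under SAP 8.1. CS abnormalities become adverse events, and individual values are listed. This stands. It would be wrong to infer that the safety analysis cannot show a direction-specific effect; the defect is confined to the shift table. Summary statistics do not replace it, because a mean change near zero is compatible with range crossings in both directions.

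**The templates may already split low and high.** They sit in a separate document (SAP 1) that was not available. The SAP text does name its three categories, so a template with a split would go beyond it.

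**A reader might infer that required re-tests are discarded and enter no table.** The documents do not say so. Protocol 11.15 never calls a re-test an unscheduled visit, the statement in Protocol 9.3.1 concerns visits rather than specimens, and SAP 8.1 begins with a qualifier. Filing under the scheduled visit is at least as natural.

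**A reader might infer that values taken after a telephone-reported AESI are systematically lost.** Protocol 11.2 requires a targeted physical examination at that visit, and Protocol 9.3.1 leaves other assessments largely to the investigator. No laboratory or vital-sign measurement is mandated. The gap arises only when one is taken, and the AESI itself reaches the AESI tables.

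**Conclusion.** The point holds as a minor one about descriptive safety tables. As written, the laboratory shift tables hide direction, and abnormal non-CS values from unscheduled visits reach no summary table. Both follow from stated rules, subject to the unseen templates. The re-test question is missing detail, not a demonstrated loss.

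It is tempting to put a number on lost baselines. With an assumed unusable-sample rate f and 353 planned subjects, 353 × f gives about 4, 7 and 18 subjects at f = 1%, 2% and 5%. The documents do not support using this as an estimate. They give no rate. The sum also assumes that every re-test is coded as unscheduled, that the narrow baseline wording is applied, and that one failed specimen removes the whole laboratory baseline, although blood count and chemistry use separate specimens (Protocol 11.15.1). Nor would those subjects leave every table: by-visit value summaries need no baseline, and the Cycle 2 evaluation has its own. The number affected is unknown and may be zero.

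No safety test is planned (SAP 8.7), and the primary and key secondary analyses are untouched.

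**What to change.** In SAP 8.1, 8.7.4 and 8.7.5, before the interim unblinding:

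1. Tabulate laboratory shifts as low/normal/high, with a CS flag beside them.
2. Add one worst post-dose shift per treatment cycle for laboratory data, with unscheduled values included as a stated exception to SAP 8.1. Because a parameter can be abnormal in either direction, show the lowest and highest values separately. For vital signs, add the same kind of summary: lowest and highest post-dose value in the cycle and its change from baseline.
3. As a clarification, analyse a re-test of an unusable sample under the scheduled visit it replaces, and let a pre-dose re-test serve as baseline.

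Items 1 and 2 change what the tables show; item 3 removes an ambiguity. The cost is SAP wording and somewhat larger descriptive safety tables. No new data are needed.

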8.2 Subject Disposition

Subject disposition information will be summarized for the double blind phase by treatment group and overall as well as separately for the open label phase. The number and percentage of subjects who are randomized, who obtained a dose of study drug, who were randomized and not treated, who were treated and not randomized, who complete the double blind treatment phase, who complete the study and who withdraw early from the study will be presented.

The primary reason for early withdrawal will also be tabulated.

Subject disposition will be listed.

The number and percentage of subjects in each analysis set will also be tabulated.

Treatment Misallocations:

If a subject was:

- Randomized but not treated, then they will be reported under their randomized treatment group. However, they will be excluded from the safety analyses as actual treatment is missing,
- Treated but not randomized, then by definition they will be excluded from the efficacy analyses since they are not randomized, but will be included in the safety analyses.
- Randomized but got incorrect treatment, then they will be reported under their randomized treatment group for all efficacy analyses, but will be reported under the treatment they actually received for all safety analyses.
- Subjects who were not treated as randomized will be excluded from the per-protocol analysis.

The visits or assessments not done as per protocol due to COVID-19 pandemic will be also listed for each subject.

8.3 Protocol Deviations

The number of subjects excluded from SAF, FAS, MFAS, and PP populations and reasons for exclusion will be summarized by treatment group and overall.

Analysis set membership details will be listed, including reason for exclusion from each analysis set.

Statistical Analysis Plan (SAP)

CROMA
est. 1976

All major protocol deviations identified will be summarized by treatment group and overall. Minor protocol deviations will be listed only.

A listing will include the inclusion/exclusion criteria violated at Screening and at Re-treatment on cycles 2, 3 and 4 as well as other protocol deviations identified based on data recorded on the electronic CRF (eCRF) and/or protocol deviation logs from [REDACTED] (based on the SAF population).

8.4 Demographics and Baseline Characteristics

8.4.1 Demographics

Age, sex, race, ethnicity, height, weight, body mass index, and Fitzpatrick skin type at baseline will be summarized descriptively by treatment group and overall using the FAS population. The FDA guideline regarding “Collection of race and ethnicity data in clinical trials” will be followed.

8.4.2 Baseline Characteristics

The categorical baseline characteristics such as baseline ECG, pregnancy test results and antibody test sample collection (yes/no) at screening will be summarized using frequency counts for the FAS population. Continuous baseline variables such as systolic blood pressure (mmHg), diastolic blood pressure (mmHg) and pulse rate (beats/min) will be summarised by descriptive statistics in the same way as continuous demographic variables for the FAS population.

8.4.3 Medical History

A summary of medical history will be presented by system organ class (SOC) and preferred term (PT) using Medical Dictionary for Regulatory Activities® (MedDRA) Version 22.0 or higher. The table will be based on the SAF population. The previous toxin treatment will be listed only.

8.4.4 Prior and Concomitant Medications

Medications used in this study will be coded by using the latest available version of the World Health Organization Drug Dictionary Standard or Enhanced and categorized as follows:

Prior medications and concomitant medications will be summarized descriptively using frequency tables by anatomical therapeutic chemical (ATC) class and preferred name by treatment group on the FAS population and presented separately for the following groups:

- Medication (recent) discontinued prior to baseline (day 0)

Statistical Analysis Plan (SAP)

CROMA
est. 1976

- Concomitant medication started at or after baseline, or started before baseline and were not discontinued prior to baseline

Details for imputing missing or partial start and/or stop dates of medication are described in Section 7.2.2.

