3.1 General Study Design

This multicenter Phase 3 study is comprised of two parts. The first part of the study is a randomized, double blind, placebo-controlled, phase which aims to demonstrate efficacy and safety of BoNT/A-DP compared with placebo. The second part is an open label extension phase to evaluate efficacy after repeat treatments and long term safety.

Subjects can receive a maximum of four treatment cycles over the duration of the study, a single treatment in the first cycle compared with placebo, and up to three subsequent treatments in the open label extension study.

Subjects between 18 and 75 years of age, inclusive with moderate to severe glabellar frown lines at maximum frown with an important psychological impact as indicated by scores >0 on either the Emotional or Social Functioning subscales of the modified Skindex-16 (GL-QoL) will be enrolled in this study. Approximately 7 sites (United States (US) and Europe) will enroll in total 353 evaluable subjects with a variety of Fitzpatrick skin types. Applying a 15% drop out rate will result in a total number of completing subjects of about 300.

[figure not shown]
The overall study scheme is presented below:

[figure not shown]
The duration of study participation for each subject will be up to 14 calendar days of screening followed by 48 to 60 weeks of treatment (re-screening will not be permitted). The first treatment cycle will be a double blinded cycle followed by up to three open label treatment cycles. Each cycle will be at least 12 weeks and can be prolonged in 4-week increments, depending on treatment effect. Re-treatment is possible until study-week 48.

	Statistical Analysis Plan (SAP)	 <small>est. 1976</small>
--	--	---

Visit Scheme/Treatment Cycle 1 (double blind)

Visit Scheme/Treatment Cycles 2, 3, 4 (open label)

Statistical Analysis Plan (SAP)

CROMA
est. 1976

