3.3 Study Treatments and Assessments

Subjects will participate in this study for a duration of 50 to 62 weeks from signing the informed consent form (ICF) to the End of Study visit (i.e., up to 14 calendar days for screening, followed by 48 to 60 weeks study participation).

Subjects will receive a maximum of four permitted rounds of treatment, with a minimum interval between treatments of 12 weeks.

The first treatment cycle of the study will comprise of two treatment groups as follows:

- Group A (active): BoNT/A-DP (20 units, 0.5 mL).
- Group B (placebo control): sterile, 0.9% sodium chloride (0.5 mL).

An interim analysis (IA) will be performed when all subjects complete the re-evaluation for retreatment visit at week 16 of the first treatment cycle or complete the double blind phase (whichever occurs earlier). Refer to Section 8.9 for more details regarding the IA.

Eligible subjects will be randomized at baseline (day 0) to Group A or B to receive the first treatment in a 3:1 randomization scheme, respectively. Investigators and subjects will be blinded to the treatment administered and will evaluate the severity of glabellar lines independently. The subjects must perform their assessment independently and ideally before the investigator, to ensure they are not biased by the investigator. The same investigator must assess the subject at baseline and at the visits at weeks 1, 2 and 4 in the first treatment cycle.

After a screening period of up to 14 calendar days, subjects will receive the first treatment (BoNT/A-DP or placebo) and attend for visits at 1, 2 and 4 weeks after treatment and at 4-

Statistical Analysis Plan (SAP)

CROMA
est. 1976

weekly intervals thereafter for evaluation of efficacy and safety (primary and key secondary efficacy endpoints will only be evaluated in the first treatment cycle in comparison with placebo). Re-screening will not be permitted.

The effect of botulinum toxin typically lasts a few months, hence the first treatment cycle will last at least 12 weeks and will end when the subjects qualify for re-treatment.

Open Label Extension

After the first treatment cycle is completed, all subjects may enter the open label extension phase and will be dosed with BoNT/A-DP (20 U) for subsequent re-treatments.

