6.2 Full Analysis Set (FAS)

The FAS includes all randomized subjects, regardless of whether they received study medication. Within the FAS, a subject will be considered for the treatment assigned by randomization and not for the treatment actually received, if different, i.e., following the intent-to-treat (ITT) principle. The FAS will be used for the evaluation of the efficacy assessments. The FAS serves as the primary efficacy analysis set.

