TEAEs and AESIs will be analyzed overall (for BoNT/A-DP or placebo), and for BoNT/A-DP treatment group additionally separately per first treatment cycle or open label extension phase: events starting on or after first treatment up to before open label extension (first cycle), and events starting on or after re-treatment until end of study (open label phase). If it cannot be determined whether an AE started during the first treatment cycle or the open label extension phase due to missing onset cycle and a partial onset date, then it will be counted as having started during the first treatment cycle. The cycle of onset as recorded in the eCRFs will be used for reported AEs by cycle where appropriate.

Events of subjects who started the first treatment with placebo but then entered the open label extension for re-treatment with BoNT/A-DP will be considered to placebo for the first cycle and to BoNT/A-DP for the open label phase.

Statistical Analysis Plan (SAP)

CROMA
est. 1976

TEAEs and AESIs (per SOC and PT) will also be summarized by seriousness, severity, relationship to study medication, and relationship to procedure using frequency counts and percentages (i.e., number and percentage of subjects with an event).

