All the above tables will be supported by associated listings.

Analysis of Safety Endpoints:

The following tables will be generated for IA:

- Overall summary of TEAEs
- Overall summary of AESIs
- Summary of TEAEs by SOC and PT
- Summary of AESIs by SOC and PT
- Summary of TEAEs by seriousness by SOC and PT
- Summary of AESIs by seriousness by SOC and PT
- Summary of TEAEs by severity by SOC and PT
- Summary of AESIs by severity by SOC and PT
- Summary of TEAEs by relationship to study medication by SOC and PT
- Summary of AESIs by relationship to study medication by SOC and PT
- Summary of TEAEs by relationship to procedure by SOC and PT
- Summary of AESIs by relationship to procedure by SOC and PT
- Summary of related TEAEs (to study medication) by SOC and PT
- Summary of related TEAEs to procedure by SOC and PT

Tables and listings will be reproduced for the final analysis as well with the double-blind and open label phases included. All the above tables will be supported by associated listings.

In addition, the following listings will be produced for the IA:

- Inclusion/exclusion criteria at randomization; this listing will not be repeated for the final analysis.
- Medical history; these listings will not be repeated for the final analysis.
- Prior and concomitant medications; this listing will be repeated for the final analysis.

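### SAP 8.4.4 counts medication that placebo-first subjects start after switching to BoNT/A-DP under placebo, because the concomitant table has no phase split

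*SAP*

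**What the plan says.** SAP 8.4.4 plans frequency tables by ATC class and "preferred name by treatment group on the FAS population and presented separately for the following groups". There are two groups. The first is medication stopped before day 0. The second is "Concomitant medication started at or after baseline, or started before baseline and were not discontinued prior to baseline". The second group has a start but no end, and nothing divides it at the first re-treatment.

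SAP 6.2 fixes what the treatment group means in this population: "a subject will be considered for the treatment assigned by randomization and not for the treatment actually received". SAP 3.3 allows every subject, including those randomised to placebo, to receive BoNT/A-DP once cycle 1 is over.

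Other sections recognise the switch. SAP 8.2 reports disposition separately for the open-label phase. SAP 8.5.1 separates exposure by phase. SAP 8.7.2 says that events of placebo starters who go on to re-treatment "will be considered to placebo for the first cycle and to BoNT/A-DP for the open label phase".

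For the interim analysis, which uses double-blind data up to week 16, SAP 8.9 names one medication output: "Prior and concomitant medications; this listing will be repeated for the final analysis". Protocol 12.4.3 asks only for coding and tabulation, and does not mention phases.

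**The concern.** Read together, SAP 8.4.4 and 6.2 give a complete rule. A drug first taken by a placebo-first subject in cycle 2, 3 or 4 appears in the placebo column, although the subject was by then on BoNT/A-DP. No other section corrects this.

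At stake is how the safety tables read side by side. The AE tables will show a true placebo column for cycle 1. The medication table next to them will show a placebo column that mixes placebo use with open-label BoNT/A-DP use. A reader who wants to see whether medication use differed between arms while the arms differed in treatment cannot do so from the planned table. Any cycle 1 difference would be diluted by the later period, in which both arms receive the same product.

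**Working it through.** **Inputs**
- Time from day 0 to the end of study, T: 48 to 60 weeks. SAP 3.1 gives "up to 14 calendar days of screening followed by 48 to 60 weeks of treatment".
- Length of cycle 1, C1: SAP 3.1 says "Each cycle will be at least 12 weeks and can be prolonged in 4-week increments". I take 12, 16 and 20 weeks.
- Dropout: 15% (SAP 5). Its timing is not given.
- COVID-19 hold on re-treatment: 16 March to 5 May 2020 (SAP 3.3), which is 50 days or 7.1 weeks.

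**The plan's own duration figure.** 2 + 48 = 50 weeks and 2 + 60 = 62 weeks. This matches the 50 to 62 weeks in SAP 3.3.

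**Share of a placebo completer's follow-up after the switch** = (T − C1)/T.

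| C1 (weeks) | T = 48 | T = 60 |
|---|---|---|
| 12 | 36/48 = 75% | 48/60 = 80% |
| 16 | 32/48 = 67% | 44/60 = 73% |
| 20 | 28/48 = 58% | 40/60 = 67% |

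The share falls to 50% only at C1 = 24 (T = 48) or C1 = 30 (T = 60).

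**Two variations at C1 = 12**
- 15% of subjects leave at week 12 (timing assumed): (0.85 × 36)/(0.85 × 48 + 0.15 × 12) = 72% for T = 48, and (0.85 × 48)/(0.85 × 60 + 0.15 × 12) = 77% for T = 60.
- Re-treatment delayed by the full hold, T = 48: (48 − 12 − 7.1)/48 = 60%.

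**Is an early switch plausible on placebo?** Protocol 4.4.2.1 gives the BLESS I placebo rates of at least 1 point improvement at week 4: 9.7% by investigator, 7.4% by subject, 1.7% by both. On either rating that is 9.7 + 7.4 − 1.7 = 15.4%, so about 85% improved on neither. For BLESS II (Protocol 4.4.2.2), 3.8 + 9.4 − 1.9 = 11.3%, so about 89%. If this persists to week 12 (assumption), most placebo subjects would still meet the FWS condition for re-treatment at the first opportunity.

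**From time to medication entries.** The table counts drugs, not weeks. Let c be the share of entries already ongoing at baseline; the documents do not give it. If new starts are spread evenly over follow-up (assumption), entries first started open-label are (1 − c) × 75% to 80%.

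| c | Share started open-label |
|---|---|
| 20% | 60% to 64% |
| 33% | 50% to 53% |
| 50% | 38% to 40% |

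The share drops below half once c exceeds 1 − 0.50/0.75 = 33% to 1 − 0.50/0.80 = 37.5%. The effect on entries is therefore not known from the documents.

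**The case against.** The case on the other side is substantial.

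- SAP 1 puts table templates in a separate document, so the phase columns may be set there. SAP 8.9 also generates baseline-characteristics output at the interim analysis, and 8.4.4 sits under that heading in the SAP, so an interim medication table is not excluded. Both points stand as possibilities. Neither changes what 8.4.4 says, and for medication 8.9 names only a listing.
- A reader might infer that no valid placebo comparison of medication can be made. The documents do not support that. The interim listing covers double-blind data, SAP 8.1 has the treatment group shown on every listing, and Protocol 11.10.1 collects start and end dates. A cycle 1 comparison can be derived. The prior-medication table is not affected at all.
- A reader might also infer that most of the medication in the placebo column was taken on BoNT/A-DP. That holds for follow-up time in the scenarios above. It is not shown for entries, because drugs ongoing at baseline are in the same category and were also taken during the placebo cycle.
- Prohibited drugs, including those affecting neuromuscular function, are already covered. SAP 6.5 and 6.6 review use of disallowed medication before interim unblinding, and 8.3 summarises major deviations by arm. Headache is covered by the phase-split AE tables. The BLESS I related headache rates of 1.9% and 0.6% are AE rates and say nothing direct about analgesic use.
- Concomitant medication is neither an objective nor an endpoint.

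These points limit the consequence. They do not remove the misattribution that follows from applying 8.4.4 as written.

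**Conclusion.** The point holds as a minor one. Applied literally, SAP 8.4.4 credits open-label medication of placebo-first subjects to placebo, out of line with the SAP's own handling of disposition, exposure and AEs, and no double-blind-only summary table is named.

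For a placebo completer, roughly 58% to 80% of follow-up time lies after the switch, assuming cycle 1 lasts 12 to 20 weeks and total follow-up is 48 to 60 weeks; a longer cycle 1 gives less. No figure can be put on the share of medication entries without knowing how many drugs were ongoing at baseline.

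The consequence is confined to a descriptive table. The primary test, the key secondary hierarchy, the analysis sets, the sample size and alpha are unaffected.

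**What to change.** In SAP 8.4.4, divide the concomitant category at the first re-treatment:

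- (a) Double-blind cycle, by randomised arm: medication taken from day 0 until before the first re-treatment.
- (b) Open-label phase, under BoNT/A-DP: medication taken from the first re-treatment on.

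Use the phase rule of SAP 8.7.2 and count a drug ongoing across the switch in both phases.

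State how partial dates are assigned to a phase. SAP 7.2.2.2 moves a start with a missing day to the first of the month, which can place an open-label start in cycle 1. It also treats a wholly missing stop date as continuing, which would carry a cycle 1 drug into the open-label table.

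If the table templates already split by phase, it is enough to say so in 8.4.4. The cost is SAP wording and one extra table from data already collected.
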